1.4 Mechanism of Action

ARCT-021, ARCT-154, and ARCT-165, each contain Arcturus' proprietary self-transcribing and -replicating RNA (STARRTM) technology, an RNA replicon construct based on the alphavirus, Venezuelan equine encephalitis virus (VEEV). The replicon for ARCT-021 (mRNA-2002) consists of a replicase gene and an RNA sequence encoding the ancestral strain SARS-CoV-2 S glycoprotein. The replicon for ARCT-165 (mRNA-2106) consists of a replicase gene and an RNA sequence encoding the SARS-CoV-2 S glycoprotein containing the SARS-CoV-2 Beta variant mutations (D80A, D215G, E484K, K417N, N501Y, and A701V) and, additionally, the D614G variant mutation. The replicon for ARCT-154 (mRNA-2105) consists of a replicase gene and an RNA sequence encoding the SARS-CoV-2 S glycoprotein containing the D614G variant mutation. The final drug product for all 3 vaccines includes an RNA replicon formulated with Arcturus' proprietary lipid nanoparticle (LNP) technology (LUNAR[®]), including 4 lipid excipients. More detail relating to these vaccines is included in the Investigator's Brochure (IB) (Arcturus 2022a).

Alphaviruses are enveloped viruses with a positive strand RNA genome. Upon infection, the genomic RNA serves as a template for translation of 4 viral nonstructural proteins that form replicase complexes. These complexes synthesize viral genomic and subgenomic RNA, the latter of which serves as a template for translation of viral structural proteins, which then assembles with genomic RNA into new infectious viral particles. By replacing the RNA coding for structural proteins with RNA coding for a protein antigen of interest (in this case, the SARS-CoV-2 full-length S glycoprotein), the self-replicating machinery of the alphavirus can be used to generate sustained expression of the antigen, making such alphavirus replicon constructs an attractive tool for vaccines. These replicon RNAs, which do not encode the complement of structural genes necessary for assembly of virus particles and do not contain reverse transcriptase that converts the RNA genome into complementary deoxyribonucleic acid (DNA), replicate exclusively in the cytoplasm and cannot introduce their genetic material into the cellular genome. A more detailed description of the mechanism of mRNA amplification and the biochemical functions for each of the nonstructural proteins is described in Rupp 2015.

On entry into the cytoplasm, the replicase gene, encoding the 4 nonstructural proteins (nsPs) (nsP1 to nsP4), is translated from mRNA, producing only the replicase proteins as a single polyprotein. The RNA-dependent RNA polymerase, nsP4, is released from the polyprotein and, in combination with the remaining nsP123 polyprotein, transcribes the complementary RNA strand of the entire mRNA, including the SARS-CoV-2 S glycoprotein RNA and poly A tail. The remaining polyprotein is processed into nsP1, nsP2, and nsP3 and, in combination with nsP4, transcribes only the 5'-G-methyl capped S glycoprotein mRNA from the 3'-5' complementary strand of mRNA. The multiple copies of S glycoprotein mRNA transcript are then translated to produce full-length S glycoprotein, which is the vaccine antigen. Cleavage of the nsP123 polyprotein into its component nsPs terminates transcription of the complementary RNA (Rupp 2015). Remaining complementary RNA and S glycoprotein mRNA are then degraded by

intracellular nucleases, thereby terminating production of the antigen. Tissue distribution studies with ARCT-021, a similar replicon RNA construct coding for the ancestral strain SARS-CoV-2 spike protein showed that the mRNA is no longer detectable in most tissues by 15 days post-dose.

During the process of self-replication, a double-stranded RNA intermediate that has immunostimulatory properties activating the innate immune system is produced, ultimately enhancing the adaptive immune response to the expressed S glycoprotein and thereby behaving as an adjuvant.

At the injection site, the LNP-formulated RNA is taken up by antigen-presenting cells and myocytes, the former of which traffic to regional lymph nodes where they present the vaccine antigen to CD4+ T cells and CD8+ T cells, resulting in their activation. Antigen can be detected in regional lymph nodes within hours of injection ([Liang 2017](#); [Lindsay 2019](#)).

Interleukin-2 from activated CD4+ T cells is subsequently important in the terminal differentiation of the activated, antigen-specific CD8+ T cells ([Zhang 2011](#)). Although the immunological events leading to antibody responses elicited by RNA vaccines have yet to be fully elucidated, T follicular helper (Tfh) cells, which are a subset of CD4+ cells, are required to develop germinal center responses and drive immunoglobulin class switch, affinity maturation, and long-term B cell memory ([Pardi 2018](#)), and strong induction of antigen-specific Tfh cells has been demonstrated following vaccination with mRNA vaccines ([Lindgren 2017](#)).

1.5 Clinical Study Experience with ARCT-165, ARCT-154, and ARCT-021

ARCT-165 and ARCT-154 are based upon similar LNP-formulated replicon RNA vaccine construct, ARCT-021. The LNP used in ARCT-021 contains the same lipids as the LNP for ARCT-165 and ARCT-154, and the RNA sequence of the replicase component of the replicon in ARCT-021 has 97% sequence homology with the replicase in ARCT-165 and ARCT-154. The principal difference in the sequences is that the mRNA in ARCT-021 codes for the ancestral strain spike protein, whereas the mRNA in ARCT-165 codes for the spike protein of the SARS-CoV-2 Beta variant, which contains the D80A, D215G, E484K, K417N, N501Y, and A701V mutations and, additionally, the D614G variant mutation; the mRNA in ARCT-154 codes for the spike protein of the ancestral strain-D614G variant. Please refer to the IB ([Arcturus 2022a](#)) for a more detailed comparison of ARCT-021, ARCT-154, and ARCT-165.

Because the principal differences between ARCT-021 and ARCT-165/ARCT-154 are primarily limited to the SARS-CoV-2 variant spike protein that is expressed, these changes only constitute a change of antigen within a platform, consistent with the “platform” approach described in [DHHS 2020](#) and [CHMP 2021](#) where, if the COVID-19 vaccine candidate is made with a platform technology used to manufacture an investigational vaccine in a previous study and is sufficiently characterized, it may be possible to use toxicology data (i.e., data from repeat-dose and biodistribution studies) and clinical data that have been obtained with other products using the same platform to support first-in-human (FIH) clinical studies. As such, Arcturus is using the non-clinical tissue distribution data, Good Laboratory Practices toxicology data, and prior human clinical study data generated with ARCT-021 to support the clinical development of ARCT-165 and ARCT-154. Please refer to the IB ([Arcturus 2022a](#)) for a description of the results of non-clinical studies conducted with ARCT-021.

At the time of finalization of this protocol (Version 3.0), 3 clinical studies had initiated evaluation of ARCT-021. These studies include a completed Phase 1/2 clinical study (ARCT-021-01) in healthy adult participants in Singapore (final report pending); an ongoing Phase 2 open-label extension study (ARCT-021-02) following on from ARCT-021-01, and a Phase 2 Study (ARCT-021-04) that is ongoing in the United States (US) and Singapore. The interim analyses of these studies, which have enrolled more than 600 participants, are described in detail in the IB. A Phase 1/2/3 study exploring ARCT-154 had initiated and fully enrolled over 19,000 participants (interim data not yet available) and the ARCT-021-04 study has administered booster doses of either ARCT-021, ARCT-154, ARCT-165 to enrolled participants (interim booster data not yet available). See Section 1.7.1 for more information.

1.6 Rationale for Dose Regimen Selection

A 2-dose priming regimen for ARCT-165 and ARCT-154 is supported by non-clinical pharmacology studies conducted in non-human primates, which showed a meaningful increase in anti-SARS-CoV-2 spike protein binding and neutralizing (sVNT) antibody titers together with broader neutralizing responses against all variants tested (SARS-CoV-2 Beta, P.1, B.1.1.7, and ancestral strain) following the second vaccination compared to the first.

A single-dose boost regimen is supported by data from multiple other vaccines where booster vaccination following the priming vaccination series is typically given as a single injection.

The 5- μ g dose level selected is supported by safety and immunogenicity data collected in the Phase 1/2 study, ARCT-021-01, which was conducted with ARCT-021 and enrolled younger (≥ 21 to < 56 years of age) and older (≥ 56 to ≤ 80 years of age) adults, and by safety data from interim analyses of the Phase 2 study, ARCT-021-04, which included 318 exposures at the 5- and 7.5- μ g doses in both younger and older adults.

Data from the Phase 1/2 study demonstrated that post-vaccination increases in binding antibody responses are observable at all doses of ARCT-021 analyzed (1-, 5-, 7.5-, and 10- μ g single-dose administration and 3- and 5- μ g administered as 2 doses). However, the 10- μ g dose was not adequately tolerated, and neutralizing antibody (plaque reduction neutralization test [PRNT50]) and T-cell responses following vaccination with ARCT-021 were most notable at the 5- and 7.5- μ g doses. Geometric mean titers (GMTs) for neutralizing antibody responses were similar at the 5- and 7.5- μ g doses, and increases in SARS-CoV-2-S-protein-stimulated T-cell responses (as assessed by enzyme-linked immune absorbent spot [ELISpot]) were similar in the participants administered doses of 5- and 7.5- μ g ARCT-021. CD8+ T-cell responses (as measured by intracellular cytokine staining [ICS]) following S-protein-peptide-pool stimulation were also similar in participants dosed with 5 μ g and 7.5 μ g of ARCT-021. However, CD4+ responses by ICS were generally greater in participants receiving 5 μ g of ARCT-021 than those receiving 7.5 μ g of ARCT-021.

ARCT-021 was generally safe and well tolerated at the 5- and 7.5- μ g doses, and the solicited and unsolicited adverse event (AE) profiles were similar at these dose levels. Given the robust immune response, the acceptable safety profile observed following administration of ARCT-021, and the important advantages to lower dose administrations of vaccine in a pandemic setting to allow for greater distribution of limited vaccine supply, the 5- μ g dose of ARCT-165 and ARCT-154 (given the similar construct to ARCT-021) offers the greatest advantages for evaluation in clinical studies.

Detailed study results are described in the IB ([Arcturus 2022a](#)).

1.7 Risk Benefit Assessment

1.7.1 Potential Risks

The potential benefits and risks of ARCT-165/ARCT-154 are informed by the non-clinical and clinical studies conducted with ARCT-021 and non-clinical pharmacology studies conducted with ARCT-165 and ARCT-154. Detailed information about the potential benefits and risks and reasonably expected AEs of ARCT-021, ARCT-154, and ARCT-165 is provided in the IB ([Arcturus 2022a](#)). A summary of the potential risks of treatment with ARCT-021, ARCT-154, and ARCT-165, together with potential mitigation for these risks, is shown in [Table 1](#). As of protocol Version 3.0, the ongoing review of safety data from the ARCT-154-01 and ARCT-021-04 had not identified any confirmed new risks with use of the ARCT-154 and ARCT-165 vaccines. However, hypertension is being evaluated as a signal based on blinded safety data from the ARCT-154-01 study.

Table 1 Risk Minimization Measures Included in Clinical Studies of ARCT-021, ARCT-154, and ARCT-165

Risk	Mitigation
Local and systemic reactogenicity	
• Vaccination via the IM route results in a lower rate of local reactions than ID or SC injection (Zhang 2015).• Local injection site reactions and systemic AEs, such as headache, fever, myalgia, or arthralgia, may be treated with acetaminophen (paracetamol), ibuprofen, or other non-steroidal anti-inflammatory drugs and/or with topical agents (e.g., ice or heat); however, administration of these agents within 24 hours prior to study vaccine administration is prohibited.• Individuals should be asked if they have a known history to any of the vaccine components prior to receiving any dose of ARCT-021, ARCT-154, or ARCT-165 vaccine. Individuals with a known severe allergy to any of these components should not be vaccinated.o ARCT-021 (frozen liquid formulation) includes nucleic acid (mRNA), four lipids (ATX-126, DSPC, cholesterol, PEG2000-DMG), [REDACTED], sucrose, [REDACTED] and sodium chloride. Note: this formulation is not in use in this study (ARCT-165-01).o ARCT-021/ARCT-154/ARCT-165 (lyophilized formulations) include nucleic acid (mRNA), four lipids (ATX-126, DSPC, cholesterol, PEG2000-DMG), sucrose, Kolliphor P188 Bio, potassium sorbate, and sodium chloride.• Allergic AEs may be treated with corticosteroids or H1/H2 blockers as indicated and if not otherwise contraindicated.• For anaphylaxis or immediate-type hypersensitivity (≤ 4 hours after injection) of at least moderate severity following the administration of the study vaccine, subsequent doses of study vaccine will not be administered.

Table 1 Risk Minimization Measures Included in Clinical Studies of ARCT-021, ARCT-154, and ARCT-165

Risk	Mitigation
VAERD if subsequently infected with SARS-CoV-2	
 In ARCT-021-04 (Phase 2 study) and in Phase 3 studies, an independent DSMB or other safety committee will assess all cases of severe COVID-19 for imbalance in order to assess the risk of VAERD. The DSMB will make recommendations concerning modifying or stopping the study in order to manage any risk(s) identified.
Myocarditis and Pericarditis	
 Participants are to be instructed to seek medical attention and notify study staff immediately should symptoms of myocarditis and /or pericarditis occur post-vaccination including chest pain, shortness of breath, or feelings of a fast-beating, fluttering or pounding heart. An unscheduled visit should be performed if feasible for further follow-up and investigation of potential myocarditis or pericarditis. Participants reporting acute chest pain, shortness of breath, palpitations, or other signs of myocarditis or pericarditis within 6 weeks after vaccination must be referred to a cardiologist for evaluation and management. Cases of myocarditis and/or pericarditis will be followed until resolution of symptoms and abnormal test findings. Individuals with a history of myocarditis, pericarditis or cardiomyopathy will be excluded from study participation. A targeted questionnaire will be utilized to conduct follow-up for potential cases of myocarditis and/or pericarditis. Participants with a reported AE/SAE of myocarditis and/or pericarditis after study vaccine administration will be excluded from receiving further doses of study vaccine. Pericarditis and/or myocarditis are considered AESIs and are thus subject to expedited reporting requirements. The investigator must notify the Sponsor within 24 hours of knowledge of any events. A single myocarditis or pericarditis event considered to be related to study vaccination will result in a study pause according to study stopping rules. 
Note: Myocarditis and/or pericarditis has not been observed with ARCT-021, ARCT-154 or ARCT-165, but has been observed with other mRNA SARS-CoV-2 vaccines.

Hypertension	
 Vital signs including blood pressure measurements are to be performed at multiple study visits including prior and following each study vaccine administration including at Days 4, 8 and 15 following any study vaccine administration to identify any clinically significant abnormalities or elevations in blood pressure. Participants with a reported AE/SAE of hypertensive crisis after study vaccine administration will be excluded from receiving further doses of study vaccine.

Table 1 Risk Minimization Measures Included in Clinical Studies of ARCT-021, ARCT-154, and ARCT-165

Risk	Mitigation
------	------------

Abbreviations: AE=adverse events; COVID-19=Coronavirus disease 2019; FDA=Food and Drug Administration; H=histamine; ID=intradermal; IM=intramuscular; SARS-CoV-2=severe acute respiratory syndrome coronavirus 2; SC=subcutaneous; Th1=T helper Type 1; Th2=T helper Type 2; VAERD=vaccine-associated enhanced respiratory disease

Other potential risks of study participation beyond those associated with study vaccine include risks relating to blood sampling and breach of confidentiality.

For currently available mRNA SARS-CoV-2 vaccines, myocarditis and pericarditis cases have been reported in males and females, most commonly within 7 days after the second dose. The incidence appears highest in males under the age of 40 and the observed risk is highest in males 12 – 17 years of age. Cases have been reported in older males and in females as well, however, and also following other doses. Symptoms of myocarditis or pericarditis include chest pain, shortness of breath, or feelings of a fast-beating, fluttering or pounding heart. Subjects should seek medical attention and also notify study staff should symptoms occur post-vaccination.

Although some reported cases required hospitalization with intensive care support, available data from short term follow-up suggest that most individuals had resolution of their symptoms with conservative management. Information is not yet available about potential long-term sequelae. It is not known whether the risk of myocarditis or pericarditis is increased following additional doses of mRNA vaccines.

Blood sampling may be associated with transient asthenia, risk of fainting, and bruising or infection at the blood sampling site. Risk of infection is reduced by cleansing of the skin prior to blood withdrawal. Risk of fainting is reduced by performing blood sampling with the participant in a seated position.

As study participation involves provision of personal health information by the participant to the site staff, measures are in place to reduce the risk of sharing of this personal information with others. Measures include maintenance of personal information in secure locations (e.g., locked file cabinets and/or password protected electronic filing systems). Only personnel involved in the conduct, oversight, monitoring, or auditing of this study will be allowed access to this personal information that is collected. All publications from this study will not disclose personal information of the participants. Study results disclosed in public locations, such as www.clinicaltrials.gov, will not include personal information of any enrolled participant.

There may be other risks, discomforts, or side effects from participation in this study that are currently unknown.

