4.2.2 Discontinuation of Study Vaccine (Participant)

4.2.2.1 Stopping Rules for Adverse Events in Individual Participants

A participant must not receive further study vaccine administrations if they experience any of the following AEs:

- Grade 3 solicited AEs (as confirmed by a blinded SRC review)
- Any anaphylactic reaction
- Severe related (possibly, probably, or definitely) unsolicited AEs
- Any clinically apparent hypersensitivity episode that is considered at least moderate in severity, is considered possibly, probably, or definitely related to study vaccine administration (as assessed by the Investigator and review of the SRC) and has the following features:
 - is not confined to the injection site
 - is immediate in onset (within ≤ 4 hours after vaccination) OR if delayed, involves more than one organ system
- Any serious adverse event (SAE) judged to be related (possibly, probably, or definitely) to study vaccine.
- Myocarditis and/or pericarditis
- Hypertensive crisis

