4.2.4 Study-Wide Pausing and Stopping Rules

If any of the following is observed in the study, further administration of study vaccine to all participants will be paused until the blinded SRC has reviewed all relevant safety data and determined that it is safe for dosing with study vaccine to resume. Termination of the study will depend on evaluation of these safety data and the findings of the SRC.

- Any SAE considered possibly, probably, or definitely related to study vaccine administration (as confirmed by SRC review)
- Any anaphylactic AE following study vaccine administration

- Any clinically apparent hypersensitivity episode that is considered at least moderate in severity, is considered probably or definitely related to study vaccine administration (as confirmed by SRC review), and has the following features:
 - Is not confined to the injection site
 - Is immediate in onset (within ≤ 4 hours after vaccination) or, if delayed, involves more than 1 organ system
- Any suspected or confirmed myocarditis, pericarditis, and/or myopericarditis event that is considered by the investigator to be possibly, probably, or definitely related to study vaccine administration or is temporally associated (within 6 weeks) with vaccine administration.
- Any death due to SARS-CoV-2 infection or any severe (per the Food and Drug Administration [FDA] criteria [[Appendix 7](#)]) SARS-CoV-2 infection in a vaccinated participant.

Events meeting Pausing Rule definitions will be referred to the SRC (which will remain blinded to the vaccine assignment), where the case details and the assessment of the event causality will be assessed. Should the SRC confirm that a Pausing Rule was met, Investigators will be immediately instructed to pause dosing, and the applicable health authorities will be notified within 1 business day of determination that a Pausing Rule has been met.

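### Protocol Table 1 and Section 4.2.2.1 give different triggers for withholding further study vaccine after non-anaphylactic hypersensitivity

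*Protocol*

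**What the plan says.** **Hypersensitivity, Table 1 (Section 1.7.1, row on local and systemic reactogenicity).** The trigger reads "For anaphylaxis or immediate-type hypersensitivity (≤ 4 hours after injection) of at least moderate severity following the administration of the study vaccine". The consequence is that "subsequent doses of study vaccine will not be administered". The only link to vaccine is timing. The entry does not mention causality, extent or delayed reactions, and it does not point to Section 4.2.2.1.

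**Hypersensitivity, Section 4.2.2.1 (individual stopping rules).** Any anaphylactic reaction is listed separately. The other hypersensitivity rule begins "Any clinically apparent hypersensitivity episode that is considered at least moderate in severity, is considered possibly, probably, or definitely related to study vaccine administration", with assessment by the Investigator and review by the SRC. The episode must also be one that "is not confined to the injection site". Its onset must be immediate, within the same 4-hour limit, "OR if delayed, involves more than one organ system".

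**Myocarditis/pericarditis pause.** Table 1 says: "A single myocarditis or pericarditis event considered to be related to study vaccination will result in a study pause according to study stopping rules". Section 4.2.4 pauses dosing for a suspected or confirmed event that the investigator considers at least possibly related, "or is temporally associated (within 6 weeks) with vaccine administration".

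**The concern.** Both hypersensitivity passages are written as instructions and both are current text. The protocol does not say which one governs. Table 1 is wider for immediate reactions and Section 4.2.2.1 is wider for delayed ones, so neither is simply a short form of the other. A site working from Table 1 and a site working from Section 4.2.2.1 could treat the same moderate reaction to dose 1 differently.

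What is at stake is whether a Cohort A participant receives the Day 29 dose. That decision feeds primary Endpoint 1c, which counts AEs leading to discontinuation of study vaccine. It also bears on membership of the Immunogenicity set (Protocol 7.2, SAP 4.2) and of the mITT set (SAP 4.2), both of which depend on the doses received.

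**Working it through.** The plan gives no figure to reproduce, so the check compares the conditions of the two passages.

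**Scope.** The event is a non-anaphylactic hypersensitivity reaction of moderate severity that is not an SAE. Anaphylaxis is left out because the passages agree on it. Severe related unsolicited AEs and related SAEs are left out because Section 4.2.2.1 stops dosing for them under other bullets.

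**Event types.** Onset has 3 levels (immediate; delayed, multi-organ; delayed, single-organ). Extent has 2 (confined to the injection site or not) and relatedness has 2 (at least possible, or unrelated). That makes 3 × 2 × 2 = 12. A multi-organ reaction cannot be confined to the injection site, which removes 2 and leaves 10.

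| Onset | Confined to site | Related | Table 1 trigger met | 4.2.2.1 trigger met |
|---|---|---|---|---|
| Immediate | No | Yes | Yes | Yes |
| Immediate | Yes | Yes | Yes | No |
| Immediate | No | No | Yes | No |
| Immediate | Yes | No | Yes | No |
| Delayed, multi-organ | No | Yes | No | Yes |
| Delayed, multi-organ | No | No | No | No |
| Delayed, single-organ | No or yes | Yes or no (4 types) | No | No |

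Both triggers are met in 1 type, Table 1 alone in 3, Section 4.2.2.1 alone in 1, and neither in 5: 1 + 3 + 1 + 5 = 10. The passages differ on 3 + 1 = 4 of the 10. This is a count of categories, not of expected participants. The documents give no rate for such reactions, so no expected number can be derived.

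**Who is affected.** Cohort A (36 of the planned 72) receives two doses and Cohort B receives one, so an individual bar on further doses has effect only in Cohort A. The arms there are 12 / 3 = 4 per vaccine in Sub-cohort A1, and 24 × 3/4 = 18 (ARCT-154) and 24 × 1/4 = 6 (ARCT-021) in Sub-cohort A2. One participant is therefore 1/4 = 25%, 1/18 = 5.6% or 1/6 = 16.7% of an arm.

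**Myocarditis/pericarditis pause.** Crossing related (yes/no) with onset within 6 weeks (yes/no) gives 4 types. The wording differs on 1: within 6 weeks but not considered related. That type meets Section 4.2.4 but not the literal Table 1 text.

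**The case against.** The strongest reply is that the two hypersensitivity passages do not collide. Each gives conditions sufficient for withholding vaccine. Neither says that doses are withheld only in those circumstances, and neither requires dosing when its own trigger is unmet. A reader might infer that the two rules cannot both be applied, or that they order opposite actions. The documents do not support that: a site could follow both by withholding whenever either trigger is met. What stands is that the protocol does not tell sites to do so, and a site using Section 4.2.2.1 alone would not know that Table 1 adds cases.

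Table 1 is also introduced as a summary of risks and mitigations across the programme, and it contains material that does not apply to this trial. That is fair. The hypersensitivity entry is nevertheless a categorical instruction, and its row is headed to include local reactions, so a site-confined reaction is within its scope.

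The 4 differing types do not carry equal weight. A moderate hypersensitivity reaction within 4 hours will seldom be judged unrelated, because Section 6.3.1.2.10 counts a reasonable temporal sequence as at least possible even where other causes could explain the event. The delayed multi-organ case is an omission from Table 1; nothing there contradicts Section 4.2.2.1. The immediate reaction confined to the injection site is the main practical gap. The Investigator or SRC may also withhold vaccine under Section 4.2.2.2 for a clinically significant condition that poses additional risk. That may catch some cases, but it does not reconcile the two texts.

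A reader might also infer that the myocarditis/pericarditis wording is a conflict of equal weight. It is not. Table 1 refers to the study stopping rules, and Section 6.3.1.2.5 regards temporally associated cases as potentially related, though in the context of expedited reporting. Potential pausing events go to a single SRC, and Table 1 and Section 4.2.2.1 agree that the affected participant receives no further doses.

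**Conclusion.** The hypersensitivity inconsistency is real and relevant to safety. The two passages differ on 4 of 10 feasible types of moderate, non-serious, non-anaphylactic reaction, and the difference runs in both directions. The case most likely to matter is an immediate moderate reaction confined to the injection site: Table 1 withholds dose 2, and the hypersensitivity trigger in Section 4.2.2.1 is not met.

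The reach is limited to Cohort A. The 25% share of a Sub-cohort A1 arm could be read as the size of the effect, but it shows only how much one participant weighs in the smallest arm; the frequency is unknown. The analyses are descriptive, so no test or error rate is affected. Consequences for Endpoint 1c and the analysis sets would follow only if such an event occurred and the choice of passage decided whether dose 2 was given.

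The myocarditis/pericarditis difference is a minor wording point, already largely covered by Table 1's reference to the stopping rules and by Section 6.3.1.2.5.

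The conclusion assumes that both passages are meant to operate in this trial. The text gives no precedence rule that would say otherwise.

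**What to change.** The sponsor and SRC should reconcile the two hypersensitivity passages, state the agreed criterion once in Section 4.2.2.1, and replace the Table 1 wording with a cross-reference to it. In the same edit, the Table 1 myocarditis/pericarditis entry should be aligned with Section 4.2.4 by cross-reference. Which clinical criterion should apply is for the sponsor and SRC to decide; none is proposed here.

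The cost is a wording change in a protocol amendment and a short note to sites and the SRC. No assessment, sample size or analysis changes.
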